10.4 Tissue Banking

Biologic specimens collected during the conduct of each clinical trial that are not used during the course of the study will be considered deliverables under the contract and thus the property of the NCI. At study completion, NCI reserves the option to either retain or relinquish ownership of the unused biologic specimens. If NCI retains ownership of specimens, the Contractor shall collect, verify and transfer the requested biologic specimens from the site to a NCI-specified repository or laboratory at NCI's expense.

11. REPORTING ADVERSE EVENTS

DEFINITION: AE means any untoward medical occurrence associated with the use of a drug in humans, whether or not considered drug related. An AE can therefore be any unfavorable and unintended sign), symptom, or disease temporally associated with participation in a study, whether or not related to that participation. This includes all deaths that occur while a participant is on a study.

Please note that all abnormal clinical laboratory values that are determined to be of clinical significance based on a physician's assessment are to be reported as AEs. Those labs determined to be of no clinical significance or of unknown clinical significance (per the physician's assessment) should not be reported as AEs. Any lab value of unknown clinical significance should continue to be investigated/followed-up further for a final determination, if possible.

A list of AEs that have occurred or might occur (Reported Adverse Events and Potential Risks) can be found in §6.2, Pharmaceutical Information, as well as the Investigator Brochure or package insert.

11.1 Adverse Events

11.1.1 Reportable AEs

All AEs that occur after the informed consent is signed and baseline assessments are completed (including run-in) must be recorded on the AE CRF (paper and/or electronic) whether or not related to study agent.

11.1.2 AE Data Elements:

The following data elements are required for adverse event reporting.

- AE verbatim term
- System Organ Class (SOC)
- Common Terminology Criteria for Adverse Events v4.0 (CTCAE) AE term
- Event onset date and event ended date
- Severity grade
- Attribution to study agent (relatedness)
- Whether or not the event was reported as a serious adverse event (SAE)
- Whether or not the subject dropped due to the event
- Outcome of the event

11.1.3 Severity of AEs

11.1.3.1 Identify the AE using the NCI Common Terminology Criteria for Adverse Events (CTCAE) version 4.0. The CTCAE provides descriptive terminology and a grading scale for each adverse event listed. A copy of the CTCAE can be found at

http://ctep.cancer.gov/protocolDevelopment/electronic_applications/ctc.htm

AEs will be assessed according to the CTCAE grade associated with the AE term. AEs that do not have a corresponding CTCAE term will be assessed according to the general guidelines for grading used in the CTCAE v4.0. as stated below.

CTCAE v4.0 general severity guidelines:

Grade	Severity	Description
1	Mild	Mild; asymptomatic or mild symptoms; clinical or diagnostic observations only; intervention not indicated.
2	Moderate	Moderate; minimal, local or noninvasive intervention indicated; limiting age-appropriate instrumental activities of daily living (ADL)*.
3	Severe	Severe or medically significant but not immediately life-threatening; hospitalization or prolongation of hospitalization indicated; disabling; limiting self-care ADL**.
4	Life-threatening	Life-threatening consequences; urgent intervention indicated.
5	Fatal	Death related to AE.

ADL

*Instrumental ADL refers to preparing meals, shopping for groceries or clothes, using the telephone, managing money, *etc.*

**Self-care ADL refers to bathing, dressing and undressing, feeding self, using the toilet, taking medications, and not bedridden.

11.1.4 Assessment of relationship of AE to treatment

The possibility that the adverse event is related to study agent will be classified as one of the following: not related, unlikely, possible, probable, definite.

11.1.5 Follow-up of AEs

All AEs, including lab abnormalities that in the opinion of the investigator are clinically significant, will be followed for at least 30 days according to good medical practices and documented as such.

11.2 Serious Adverse Events

11.2.1 DEFINITION: Fed. Reg. 75, Sept. 29, 2010 defines SAEs as those events, occurring at any dose, which meet any of the following criteria:

- Results in death
- Is life threatening (*Note: the term life-threatening refers to an event in which the patient was at risk of death at the time of the event; it does not refer to an event which hypothetically might have caused death if it were more severe*).
- Requires inpatient hospitalization or prolongation of existing hospitalization
- Results in persistent or significant incapacity or substantial disruption of the ability to conduct normal life functions
- Is a congenital abnormality/birth defect
- Important medical events that may not result in death, be life-threatening or require hospitalization may be considered serious when, based upon appropriate medical judgment, they may jeopardize the patient or subject and may require medical or surgical intervention to prevent one of the outcomes listed.

11.2.2 Reporting SAEs to DCP

11.2.2.1 The Lead Organization and all Participating Organizations will report SAEs on the DCP SAE form found at http://prevention.cancer.gov/files/clinical-trials/SAE_form.doc.

11.2.2.2 Contact the DCP Medical Monitor by phone within 24 hours of knowledge of the event.

[name], MD
Lung and Upper Aerodigestive Cancer Research Group
Division of Cancer Prevention, NCI, NIH
[name]
[name]
[contact]
[contact]
[contact]

Include the following information when calling the Medical Monitor:

- Date and time of the SAE
- Date and time of the SAE report
- Name of reporter
- Call back phone number
- Affiliation/Institution conducting the study
- DCP protocol number
- Title of protocol
- Description of the SAE, including attribution to drug and expectedness

11.2.2.3 The Lead Organization and all Participating Organizations will FAX or email written SAE reports to the DCP Medical Monitor within 48 hours of learning of the event using the paper SAE form. The written SAE reports will also be faxed [contact]) or emailed ([contact]) to DCP's Regulatory Contractor, CCS Associates ([contact]).

11.2.2.4 The DCP Medical Monitor and regulatory staff will determine which SAEs require FDA submission.

11.2.2.5 The Lead Organization and all Participating Organizations will comply with applicable regulatory requirements related to reporting SAEs to the IRB/IEC.

11.2.3 Follow-up of SAE

Site staff should send follow-up reports as requested when additional information is available. Additional information should be entered on the DCP SAE form in the appropriate format. Follow-up information should be sent to DCP as soon as available. SAE related to the study agent will be followed until resolved, or deemed unlikely to further resolved by the Protocol Chair, or until the subject withdraws consent for further follow-up. SAE unrelated or unlikely to be related to study agent will be followed for at least 30 days after the last dose of study agent.

12. STUDY MONITORING

12.1 Data Management

This study will report clinical data using the OnCore application from Forte Research Systems, Inc., as stated in the Master Data Management Plan. All users of the database will have appropriate education, training and experience to perform assigned tasks. The data collection and management will be done according to the Consortia 2012 DMP.

12.2 Case Report Forms

Participant data will be collected using protocol-specific case report forms (CRF) developed from the standard set of DCP Chemoprevention CRF Templates and utilizing NCI-approved Common Data Elements (CDE). The approved CRFs will be used to create the electronic CRF (e-CRF) screens in the OnCore application. Consortia site staff will enter data into the e-CRF for transmission to DCP according to pre-established DCP standards and procedures. Amended CRF will be submitted to the DCP Protocol Information Office for review and approval. Approved changes will be programmed into the OnCore database by the Consortium Data Management staff.

CRF Submission Information:

University of Arizona Early Phase Chemoprevention Consortium Office
Attn: [name]
[name]
[name]
[contact]
[contact]
Email: [contact]

12.3 Source Documents

Source documentation for this trial will consist of protocol-specific source documents as well as clinical and research laboratory reports. In the event of a Serious Adverse Event, medical records related to the event will be sought for source documentation of the event and its treatment, if any.

12.4 Data and Safety Monitoring Plan

The University of Arizona Cancer Center (UACC) Data and Safety Monitoring Board (DSMB) will provide oversight for subject safety for all UA Consortium clinical trials consistent with the National Institutes of Health Policy for Data and Safety Monitoring dated June 10, 1998; further guidance statement issued by the NIH on June 5, 2000, and the policy for Data and Safety Monitoring by Data and Safety Monitoring Boards. The UACC DSMB meets quarterly.

Regular monthly meetings of the UA Consortium, are used as a forum to review accrual rates, problematic issues relating to accrual and protocol implementation, adverse events occurrence, follow-up, and reporting; submission of all required study reports; and progress and outcomes of laboratory analyses.

12.5 Sponsor or FDA Monitoring

The NCI, DCP (or their designee), pharmaceutical collaborator (or their designee), or FDA may monitor/audit various aspects of the study. These monitors will be given access to facilities, databases, supplies and records to review and verify data pertinent to the study.

12.6 Record Retention

Clinical records for all participants, including CRFs, all source documentation (containing evidence to study eligibility, history and physical findings, laboratory data, results of consultations, *etc.*), as well as IRB records and other regulatory documentation will be retained by the Investigator in a secure storage facility in compliance with Health Insurance Portability and Accountability Act (HIPAA), Office of Human Research Protections (OHRP), Food and Drug Administration (FDA) regulations and guidances, and NCI/DCP requirements, unless the standard at the site is more stringent. The records for all studies performed under an IND will be maintained, at a minimum, for two years after the approval of a New Drug Application (NDA). For NCI/DCP, records will be retained for at least three years after the completion of the research. NCI will be notified prior to the planned destruction of any materials. The records should be accessible for inspection and copying by authorized persons of the Food and Drug Administration. If the study is done outside of the United States, applicable regulatory requirements for the specific country participating in the study also apply.

12.7 Cooperative Research and Development Agreement (CRADA)/Clinical Trials Agreement (CTA)

Not applicable.

13. STATISTICAL CONSIDERATIONS

13.1 Study Design/Description

This study utilizes a Phase II double-blind, randomized, placebo controlled design to assess the effect of PROSTVAC® in patients with clinically localized prostate cancer undergoing active surveillance. Each eligible participant will be randomly assigned to receive either PROSTVAC® or matched placebo. Due to potential withdrawals and the absence of tumor in the post-intervention biopsy, 25% or more participants may not provide endpoint data. All of the statistical analysis (both primary and secondary analysis) will be based on the intent-to-treat principle. Multiple imputation (MI) techniques will be applied, as necessary, for participants without endpoint data. The statistical analysis based on Rubin's rules will be performed on the imputed datasets, if MI is performed.

13.2 Randomization/Stratification

We plan to randomize 150 eligible participants to receive either PROSTVAC® or matched placebo at a 2:1 ratio (i.e. 100 receiving PROSTVAC® and 50 receiving placebo) based on a random allocation rule. Blocking technique with a size of 3 or 6 will be used to assure a 2:1 ratio between PROSTVAC® and placebo. In addition, randomization will be stratified by the study site and the number of repeat biopsy following diagnosis (≤ 2 or > 2).

13.3 Accrual and Feasibility

We plan to randomize 150 eligible participants. We anticipate to enroll 6-8 participants/per month and estimate that it will take approximately 20-25 months to complete accrual.

13.4 Primary Objective, Endpoint(s), Analysis Plan

The primary objectives of this study are to determine the effects of PROSTVAC® on the change (from pre- to post-intervention) in CD8⁺ and CD4⁺ positive cells in the stroma adjacent to tumor and within the malignant portion of the prostate biopsies.

The primary endpoints are the change in CD8⁺ and CD4⁺ positive cells in the stroma adjacent to tumor and within the malignant portion of the prostate biopsies. The change in CD8⁺ and CD4⁺ positive cells will be compared between participants treated with PROSTVAC® and those treated with placebo. We project an attrition rate of 10% (with respect to completing the intervention and providing post intervention biopsy) and 70% of the post intervention biopsy would have tumor. We plan to randomize 150 eligible participants to receive PROSTVAC® or placebo at a 2:1 ratio to have 63 and 31 subjects in the PROSTVAC® group and the placebo group, respectively, with primary endpoint data. A two-sided two-sample t test will be used to compare the change in CD4⁺ and CD8⁺ positive cells in tumor tissue between the treatment and placebo groups. Based on a sample size of 63 in the PROSTVAC® group and 31 in the placebo group and assuming that the standard deviation of the change in CD8⁺ and CD4⁺ positive cells for the PROSTVAC group is twice that of the placebo group, the power will be at least 90% to detect a Cohen's d effect size (i.e. the difference between the two groups divided by the pooled standard deviation) of ≥ 0.63 at a significance level of 5% by the Bonferroni correction (i.e., a significance level of 2.5% for each). MI techniques will be performed, as needed, for the participants without endpoint data. If MI is deemed necessary, the variables that are predictive of missing endpoint data will be incorporated into MI. The "available" sample size after MI is expected to be larger than the estimated sample size. Hence, we are confident of detecting effect sizes smaller than the above effect sizes after applying the Rubin's rules since the predictive variables used in MI can improve efficiency and reduce potential bias due to missing data.

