4. PARTICIPANT SELECTION

4.1 Inclusion Criteria

- 4.1.1 Biopsy-proven (consisting of ≥ 10 tissue cores) adenocarcinoma of the prostate with cancer present in at least one biopsy core, either random or targeted, in the most recent biopsy.
- 4.1.2 All prior biopsies must meet the following: $\leq 50\%$ of the total number of random biopsy cores positive for cancer
 - Gleason score $\leq (3+4)$
- 4.1.3 Clinical stage $\leq T2a$ by DRE
- 4.1.4 Biopsies performed at outside institutions should have Gleason score confirmed at the study site by a GU pathologist to ensure eligibility.
- 4.1.5 Pre-intervention biopsy tissue (most proximal to enrollment) containing sufficient tumor tissue to cut 5-10 unstained slides confirmed to be available upon request.
- 4.1.6 Screening serum PSA < 20 ng/mL. For men treated with 5-alpha-reductase inhibitors (e.g., finasteride, dutasteride), PSA needs to be < 10 ng/mL.
- 4.1.7 Hematological eligibility parameters:
Neutrophil count $\geq 1,200/\text{mm}^3$ (≥ 1.2 k/ μL)
Stable platelet count $\geq 75,000/\text{mm}^3$ (≥ 75 k/ μL)
- 4.1.8 Hepatic and renal function eligibility parameters:
Bilirubin ≤ 1.5 mg/dL (or ≤ 3.0 mg/dL for patients with Gilbert's syndrome)
ALT and AST ≤ 2.5 x ULN
Serum creatinine ≤ 1.5 x ULN
- 4.1.9 Karnofsky $\geq 70\%$; see Appendix A.
- 4.1.10 Must agree to use medically acceptable barrier and/or chemical method of contraception while on study and for at least one month following the last vaccine injection because the effects of PROSTVAC® on the developing human fetus at the recommended therapeutic dose are unknown. Should a participant's partner become pregnant or suspect she is pregnant while the participant is participating in this study, the study physician should be informed immediately. In the event a participant's partner becomes pregnant, the study sponsor may request additional information regarding the course of the pregnancy and if the pregnancy is carried to term, the birth of the child (i.e., the outcome of the pregnancy).
- 4.1.11 Ability to understand and the willingness to sign a written informed consent document.
- 4.1.12 No planned prostate biopsies during the intervention until after the post-intervention biopsy.
- 4.1.13 Men on stable doses of 5-alpha reductase inhibitors are eligible as long as there is no planned dose change while on study.

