13.5 Secondary Objectives, Endpoints, Analysis Plans

The secondary objectives are to determine the effects of PROSTVAC® on the change in PD-L1 positive cells in the stroma adjacent to tumor and within the malignant portion of the prostate biopsies, the correlation between the change in CD8⁺ and the change in PSA, to determine the effect of PROSTVAC® on the change in CD8⁺, CD4⁺, and PD-L1 positive cells in the benign portion of the prostate biopsies, to determine the effect of PROSTVAC® on the change in PSA, to assess the effect of PROSTVAC® on tumor grade and tumor extent, to assess the proportion of men with no cancer on the post-intervention biopsy, to assess the safety and feasibility of PROSTVAC®, and to assess the effects of PROSTVAC® on LUTS.

The secondary endpoints include the change in PD-L1 positive cells in the stroma adjacent to tumor and within the malignant portion of the prostate biopsies, the correlation between the change in CD8⁺ and the

change in PSA, the change in CD8⁺, CD4⁺, and PD-L1 positive cells in the benign portion of the prostate biopsies, the change in PSA, the tumor grade progression, the change in tumor extent, safety and feasibility, and the change in International Prostate Symptom Score. In addition, a comparison will be made between the two study arms on the proportion of patients with no cancer on the post-intervention biopsy. Similarly, MI techniques will be performed, as necessary. A two-sided two-sample t test at a significance level of 5% will be performed to compare each of the secondary endpoints between the PROSTVAC® and placebo groups. Pearson correlation coefficient will be derived to evaluate the correlation between the change in CD8⁺ and the change in PSA for participants treated with PROSTVAC®. Fisher's exact test will be performed to compare the proportion of patients with no cancer on the post-intervention biopsy and the proportion of men with an increase in Gleason score to $\geq 4+3$ between the two groups. These secondary analyses are considered exploratory, therefore, no correction will be performed for multiple comparisons.

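### The primary t test on change scores uses neither an estimated baseline slope nor the randomisation strata: valid, but an adjusted model could cut the variance by about 0–18% under the plan's own SD assumption

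*Combined protocol and SAP*

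**What the plan says.** All references are to the combined protocol and SAP.

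- **Primary test (Section 13.4).** "A two-sided two-sample t test will be used to compare the change in" CD4+ and CD8+ cells between the arms. The error rate is set "at a significance level of 5% by the Bonferroni correction (i.e., a significance level of 2.5% for each" endpoint.
- **Power (Section 13.4).** "the power will be at least 90% to detect a Cohen's d effect size", defined as "the difference between the two groups divided by the pooled standard deviation) of ≥ 0.63". This assumes 63 and 31 evaluable men and a standard deviation of change in the vaccine arm twice that in the placebo arm.
- **Secondary endpoints (Section 13.5).** "A two-sided two-sample t test at a significance level of 5% will be performed to compare each of the secondary endpoints". Fisher's exact test is added for two proportions, and the analyses are labelled exploratory. The closing paragraphs add a transformation, a rank-test fallback and an outlier sensitivity analysis.
- **Randomisation (Section 13.2).** "randomization will be stratified by the study site and the number of repeat biopsy following diagnosis", with a cut at two repeat biopsies.
- **Baseline tissue (Section 4.1, item 4.1.5).** Entry requires "Pre-intervention biopsy tissue (most proximal to enrollment) containing sufficient tumor tissue", confirmed to be obtainable.

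No ANCOVA or stratified analysis appears anywhere. Section 13.4 credits predictive variables with improving efficiency, but uses them only inside multiple imputation, which is itself conditional.

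**The concern.** The change endpoint cannot be computed without the pre-intervention measurement, so adjusting for it needs no extra data. Subtracting it is one particular adjustment, with the slope set at 1. When the true slope is below 1, subtraction carries too much of any chance baseline difference into the treatment estimate, and the standard error grows accordingly.

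A low slope is plausible here. The pre-intervention biopsy is the latest one before enrolment, and item 4.1.5 sets no maximum age. Section 10.2 takes one or two blocks per time point. Section 3 allows either TRUS-guided or fusion-targeted sampling after the intervention.

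The strata are a separate matter. The design balances arms within site and repeat-biopsy group, but the planned standard error takes no credit for that balance.

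At stake is precision on both primary endpoints and on any continuous secondary endpoint with a baseline value. The argument for a low slope concerns biopsy cores. It is not established for PSA or IPSS, for which the documents give no correlation.

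**Working it through.** **Inputs.** From Sections 13.2 and 13.4: 100 and 50 randomised, 10% attrition, 70% of later biopsies with tumor, two-sided alpha 0.025 per endpoint, d = 0.63, ratio of SDs of change 2:1. Assumed, because the documents do not give it: pre–post correlation ρ of 0.3, 0.5 or 0.7.

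**1. The plan's own figure.** Evaluable men: 100 × 0.9 × 0.7 = 63, and 50 × 0.9 × 0.7 = 31.5, taken as 31. Set the SDs of change to 2 and 1.
- Weighted pooled SD = √[(62×4 + 30×1)/92] = 1.738, so the difference is 0.63 × 1.738 = 1.095.
- Variance of the treatment difference = 4/63 + 1/31 = 0.09575, so SE = 0.3094.
- 1.095/0.3094 = 3.539. Power = Φ(3.539 − 2.241) = 90.3% (89.4% with the noncentral Welch t).

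The stated 90% reproduces, given an unequal-variance test. Section 13.4 does not say which form of t test is meant. In 200,000 simulated trials with 2:1 SDs, the pooled-variance form had 76.7% power and a type I error of 0.6% against the nominal 2.5%.

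**2. Equal SDs in both arms and at both times.** Variance of change is 2s²(1−ρ) and ANCOVA residual variance is s²(1−ρ²). The ratio is (1+ρ)/2, so the reduction is (1−ρ)/2: 35%, 25% and 15%. The planned test at d = 0.63 has SE √(1/63 + 1/31) = 0.2194 and power Φ(0.63/0.2194 − 2.241) = 73.6%. ANCOVA gives 90.7%, 85.9% and 80.9%.

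**3. The plan's 2:1 SDs of change.** Scale the placebo variance of change to 1. The gain depends on how the extra vaccine-arm variance arises.

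- **A. Extra variance independent of baseline.** Adjustment removes r = (1−ρ)/2 from each arm: V = (4−r)/63 + (1−r)/31 = 0.0789, 0.0837, 0.0885.
- **B. Same ρ in both arms.** Baseline variance is s² = 1/[2(1−ρ)]. The vaccine-arm post SD σ solves σ² − 2ρsσ + s² = 4, and that arm's slope is ρσ/s. At ρ = 0.7, s² = 1.667 and σ = 2.679, so the slopes are 1.452 (vaccine) and 0.700 (placebo).
- **C. Equal pre and post SDs in both arms.** The ρ shown is the vaccine arm's. The placebo arm's then has to be 0.825, 0.875 or 0.925.

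The common slope is weighted 63:31. The arm-specific figures include the variance from estimating the centring mean, (slope difference)² × s²/94.

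| Reduction in variance | ρ = 0.3 | ρ = 0.5 | ρ = 0.7 |
|---|---|---|---|
| A (slopes equal) | 17.6% | 12.6% | 7.5% |
| B, common slope | 10.3% | 1.6% | −5.3% |
| B, arm-specific slopes | 11.1% | 4.1% | 0.2% |
| C, common slope | 12.8% | 9.2% | 5.5% |
| C, arm-specific slopes | 17.4% | 12.4% | 7.5% |

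In case A the detectable d is 0.63 × √(V/0.09575) = 0.57, 0.59, 0.61, and power at 0.63 is 95.1%, 93.9%, 92.5% against 90.3%. In case B with a common slope and ρ = 0.7, power falls to 88.6%.

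**4. Chance imbalance.** With 63 and 31 men, the standard error of the baseline mean difference is 0.22 baseline SDs.

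**5. Strata.** The documents give no association between either factor and the endpoints, and the available text does not state the number of sites. No gain can be computed.

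**The case against.** The strongest defence is that a two-sample test on change is valid under randomisation, answers the stated objective directly and has fallbacks for non-normal data. The secondary analyses are declared exploratory. Adjustment is then a preference about efficiency, with an unknown gain. All of this stands, and it limits how far the point can be pressed.

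A reader might infer three stronger things that the documents do not support.

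- **That the plan ignores baseline or leaves imbalance uncorrected.** It does neither. Subtraction uses the baseline with a coefficient of 1 and may correct too much.
- **That 15–35% of the variance is given away, bringing the detectable d down to 0.51–0.58.** Those percentages need equal SDs across arms and time points, whereas Section 13.4 assumes 2:1 for change. The 0.63 reproduces only under 2:1, so multiplying it by an equal-SD factor combines two incompatible models.
- **That omitting the strata invalidates the test.** Leaving stratification factors out of the analysis generally makes it conservative.

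The objection also bears on the remedy. A common-slope ANCOVA can do slightly worse than the planned test, and with 31 evaluable placebo men, site terms are not obviously free.

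**Conclusion.** The point holds as a question of efficiency. The primary test fixes the baseline slope at 1 and uses neither randomisation stratum. No error rate or estimand is compromised.

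Under the plan's 2:1 assumption and an assumed ρ of 0.3 to 0.7, adjustment with arm-specific slopes reduces the variance of the treatment difference by about 0–18%. A common slope gives about −5% to 18%. If the SDs are in fact equal, the reduction is 15–35%. That case matters because the planned test then has only about 74% power at d = 0.63, which ANCOVA raises to about 81–91%. These ranges rest on the assumed ρ and on the three variance structures examined. No part of them comes from the strata.

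The change is worth making: its data cost is nil, and Section 13.9 has the primary endpoints analysed in batches at the end of the study, which leaves room to settle the wording before those results exist.

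**What to change.** In Section 13.4, pre-specify as primary, for each of CD8+ and CD4+:

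- ANCOVA of the post-intervention value (on the transformed scale if a transformation is used) on arm, pre-intervention value, repeat-biopsy stratum and site. Pool small sites by a rule fixed before unblinding.
- A baseline-by-arm term, with baseline centred at the overall mean of the men analysed. This protects against the common-slope loss in case B.
- Heteroscedasticity-robust (HC3) standard errors. HC3 treats the centring mean as fixed. State whether its variance is added: in case B at ρ = 0.7 the term is (1.452 − 0.700)² × 1.667/94 = 0.010, against a total of about 0.096.
- The Welch test on change as a sensitivity analysis, named as the unequal-variance form.

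Use the same model in Section 13.5 for continuous secondary endpoints that have a baseline value. Quote any expected gain as a function of an assumed ρ.

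The cost is SAP wording and a few degrees of freedom, more if many sites remain after pooling. No new data are needed.

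### The 90% power in section 13.4 depends on an unequal-variance t test that the plan does not name; a pooled-variance test, equally allowed by the wording, has about 76%

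*Combined protocol and SAP*

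**What the plan says.** Section 13.4 gives the primary analysis and its power in one paragraph.

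- **Test:** "A two-sided two-sample t test will be used to compare the change in CD4⁺ and CD8⁺ positive cells in tumor tissue". It does not say whether the two variances are pooled.
- **Level:** Bonferroni over CD8+ and CD4+, that is "a significance level of 2.5% for each".
- **Numbers:** "Based on a sample size of 63 in the PROSTVAC® group and 31 in the placebo group".
- **Spread:** the SD of the change in "positive cells for the PROSTVAC group is twice that of the placebo group". No source is given.
- **Effect and power:** "the power will be at least 90% to detect a Cohen's d effect size" of at least "0.63 at a significance level of 5% by the Bonferroni correction", where d is the mean difference divided by the pooled SD.

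The last part of section 13.5 covers the primary endpoints too. It provides for non-normality (transformation, then a rank test) and for outliers, but not for unequal variances.

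**The concern.** The power statement and the test description do not fully fit together. The power is calculated with unequal SDs, while the test is named in a form that many analysts would run with a pooled variance. Under the plan's own assumptions that choice matters. When the larger arm also has the larger variance, the pooled standard error is too big and the test becomes conservative.

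Two things are at stake. First, an analyst could follow section 13.4 to the letter, run the pooled test on both primary endpoints, and have much less power than stated; a null result would then be read against 90% power that the analysis did not have. Second, if the form is left open until the data are seen, the choice between the two becomes a data-dependent decision on the primary analysis.

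**Working it through.** **Inputs (all from section 13.4 unless noted).** n1 = 63, n2 = 31; two-sided alpha 0.025 per endpoint; SDs in ratio 2:1, set to 2 (PROSTVAC) and 1 (placebo); d = 0.63. The evaluable numbers follow from the randomized 100 and 50 (section 13.2), 10% attrition and 70% of biopsies with tumor: 100 × 0.9 × 0.7 = 63 and 50 × 0.9 × 0.7 = 31.5, taken as 31.

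**Step 1. The difference implied by d.** Pooled SD weighted by degrees of freedom = sqrt((62 × 4 + 30 × 1)/92) = 1.738. Difference = 0.63 × 1.738 = 1.095.

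**Step 2. Reproduce the plan's figure with the Welch test.**
- Standard error = sqrt(4/63 + 1/31) = 0.309.
- Noncentrality = 1.095/0.309 = 3.54; Satterthwaite df about 92; critical value 2.28.
- Power = 89.4% by noncentral t, and 89.4% by simulation (400,000 runs).
- Normal approximation: Phi(3.54 − 2.24) = 90.3%.

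The stated 90% is therefore reproduced within 0.6 points. The d that gives 90% exactly is 0.636.

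**Step 3. Same inputs, pooled-variance test.**
- Pooled standard error, at the expected variance = 1.738 × sqrt(1/63 + 1/31) = 0.381.
- True standard error of the difference = 0.309, so the test overstates it by a factor of 0.381/0.309 = 1.23.
- Simulation (400,000 runs): power 76.4%; rejection rate with no true effect 0.6% against the nominal 2.5%. Welch in the same null setting rejects 2.5%.
- The pooled test reaches 90% power at d of about 0.73 to 0.74.

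The gap between the forms is 89.4 − 76.4 = 13 points on each primary endpoint.

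**Step 4. Sensitivity to the SD ratio (Welch, d = 0.63, same pooled-SD definition, noncentral t).**

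| PROSTVAC SD : placebo SD | Power |
|---|---|
| 1:1 | 71.6% |
| 1.5:1 | 83.9% |
| 1.75:1 | 87.2% |
| 2:1 | 89.4% |
| 2.25:1 | 91.0% |
| 2.5:1 | 92.0% |
| 3:1 | 93.4% |

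At 1:1 the pooled test gives 72.3%, so with equal SDs the form of the test hardly matters.

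**Step 5. Sensitivity to the definition of d.** If pooled SD meant the root mean square of the two SDs (1.581), the same d would give 82.5% with Welch and 65.9% with the pooled test. The version weighted by degrees of freedom is the usual meaning and the one that reproduces the plan's figure.

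**The case against.** The strongest reply is that nothing in section 13.4 says pooled, equal-variance or Student. Welch is a two-sample t test, and a plan that assumes unequal SDs is most coherently read as intending it. On that reading the stated power is reproduced. The pooled test's fault is also conservative: it adds no false-positive risk, and it arises only if that form is run and the SDs really differ as assumed. Section 13.5 may in any case lead to a transformation or a rank test.

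Most of this stands, and it rules out three stronger conclusions that a reader might draw.

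- *That 90% holds for no form of the named test, or is an arithmetic mistake.* It is not: 89.4% exact and 90.3% by normal approximation are consistent with rounding or an approximate formula.
- *That the equal-SD figure of about 72% contradicts the plan.* It drops the plan's stated SD assumption, so it is only a sensitivity result.
- *That the figure needs a ratio of exactly 2:1.* Welch power is 91.0% at 2.25:1 and 93.4% at 3:1. The documents do not show whether a ratio below or above 2 is more likely.

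What the reply does not remove is that the coherent reading has to be inferred. Neither 13.4 nor 13.5 selects it, and an analyst running the classical pooled test would still comply with the plan.

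**Conclusion.** The concern holds as a gap in the test specification. Under the plan's own inputs the form of the t test moves power at d = 0.63 from about 89% to about 76% on both primary endpoints, and moves the actual type I error from 2.5% to about 0.6%. The stated power belongs to the Welch form only.

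This rests on approximately normal changes, 63 and 31 participants with endpoint data, the 2:1 SD ratio with the larger SD in the larger arm, and d defined by the pooled SD weighted by degrees of freedom. The ratio has no source in the documents, so the power should be shown over a range. Severity: should-fix.

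**What to change.** In section 13.4:

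1. Name the unequal-variance (Welch) two-sample t test as the primary test for both CD8+ and CD4+.
2. Restate the power as about 89% at d = 0.63, or 90% at d of about 0.64, and say that d uses the pooled SD weighted by degrees of freedom.
3. Label the 2:1 SD ratio as an assumption, and give Welch power on both sides of it at d = 0.63: about 72% at 1:1, 84% at 1.5:1, 89% at 2:1, 92% at 2.5:1 and 93% at 3:1.

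Make the change before unblinding, so that the form of the test is not chosen on the data. The cost is wording only: no change to sample size, conduct or data collection. The one downside is a slightly less favourable stated power.
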